7.1.4 Overall Survival

Overall Survival (OS) is calculated from the date of randomization up to the date of death (any cause). For patients still alive or lost to follow-up at the time of analysis, survival will be censored at last follow-up visit date.

7.1.5 Overall response

All patients included in the study must be assessed for response to treatment, even if there is a major protocol treatment deviation or if they are ineligible, or not followed/re-evaluated. Each patient will be assigned one of the following categories: complete response, partial response, stable disease, progressive disease, early death or not evaluable. Early death is defined as any death occurring before the first per protocol time point of tumor re-evaluation.

Patients' response will be classified as "not evaluable" if insufficient data were collected to allow evaluation per these criteria.

7.1.6 Best overall response

Best overall response is the best response designation recorded from the date of randomization until disease progression.

7.1.7 Response duration

Objective response duration (CR/PR) and complete response (CR) will be measured similarly to PFS (see above) but starting from the time measurement criteria for CR/PR or CR (whichever is first recorded) are first met.

7.2 Evaluation of safety

7.2.1 Adverse events

All adverse events will be recorded; the investigator will assess whether those events are drug related (reasonable possibility, no reasonable possibility) and this assessment will be recorded in the database for all adverse events.

Only the worst grade per CTCAE category will be recorded per cycle. The collection period will start from randomization up to 30 days after administration of the last dose of protocol treatment or until the start of a new antitumor therapy, whichever occurs first.

All adverse events must be followed until resolution or stabilization.

Whenever possible, the Investigator will record the main diagnosis instead of the signs and symptoms normally included in the diagnoses.

Investigators must pursue and obtain information adequate both to determine the outcome and to assess whether it meets the criteria for classification as a SAE requiring immediate notification.

7.2.2 General evaluation of adverse events

This study will use the International Common Terminology Criteria for Adverse Events (CTCAE), version 4.0, for adverse event reporting. A copy of the CTCAE can be accessed from the EORTC home page www.eortc.org/investigators-area/ctc.

The highest CTCAE grading per cycle and per patient will be computed at the EORTC HQ for analysis.

Planned safety analysis and tabulations are described in the statistics section.

7.2.3 Serious adverse events

Serious adverse events are defined by the Good Clinical Practice Guideline.

**SERIOUS ADVERSE EVENTS SHOULD BE IMMEDIATELY REPORTED
ACCORDING TO THE PROCEDURE DETAILED IN THIS PROTOCOL** (see chapter 15 on
Reporting Serious Adverse Events)

7.2.4 Toxic deaths

Toxic death is defined as death due to toxicity (defined as adverse events at least with reasonable possibility related to study treatment). The cause of death must be reported as "toxicity".

The evaluation of toxic deaths is independent of the evaluation of response (patients can die from toxicity after a complete assessment of the response to therapy).

7.2.5 Evaluability for safety

All patients who have started the treatment will be included in overall safety analyses.

For hematological events, the medical review team may decide that blood counts have not been performed and/or reported according to the protocol and are therefore inadequate for the evaluation of one/several hematological parameters in some patients.

Patients who have discontinued treatment because of toxicity will always be included in the safety analyses.

8 Statistical considerations

8.1 Statistical design

8.1.1 Sample size

This trial is a phase II with a Korn superiority design comparing PFS between trabectedin and control with a treatment allocation ratio equal to 2:1 at randomization. Based on RANO recommendation (Ref. 1), PFS-6=15% was assumed in the control arm and 35% in the trabectedin arm (i.e. 20% difference). Assuming PFS follows an exponential distribution, this corresponds to a treatment Hazard Ratio (HR) equal to 0.55. Based on the logrank test, a type I error equal to 10% one-sided (20% two sided), a power equal to 85%, 72 progressions or deaths are needed to assess the targeted effect. 86 eligible patients who started their treatment (per protocol population) should be recruited (57 trabectedin, 29 control). Assuming 7.17 patients per month (1.99 months 0-4, 3.55 months 4-8, 5.29 months 8-12 and 7.17 beyond 12 months), about 18 months of recruitment are needed. Events should be observed shortly (about 3-4 months) after end of accrual.

8.1.2 Randomization and stratifications

All patients entered will be centrally randomized at the EORTC Headquarters (for practical details, see chapter on randomization procedure). The minimization technique (Ref. 12) used by the EORTC for random treatment allocation is based on the variance method with semi-random assignment dependent on a preset threshold, as implemented by Freedman and White (Ref. 13). However, per suggestion of the ICH E9 statistical guidelines, the algorithm has been modified to incorporate a random allocation component in order to ensure an additional 15% of completely random assignments. In this trial, the threshold is set to 4, the total number of stratification factors. Stratification factors are: institution, pathological grade (II, III), age ($\leq, > 60$) and performance status (0, >0).

8.2 Statistical analysis plan

8.2.1 Primary and secondary endpoints

8.2.2 Analysis populations

- ◆ Intention-to-treat population: all randomized patients will be analyzed in the arm they were allocated by randomization
- ◆ Per protocol population: all patients who are eligible and have started their allocated treatment (at least one dose of Trabectedin or start of local standard of care therapy)
- ◆ Safety population: all patients who have started their allocated treatment (at least one dose of Trabectedin or start of local standard of care therapy)

A patient will be considered to be eligible if the patient did not have any deviation from the patient selection criteria listed in chapter 3 of the protocol. Potential eligibility problems will be assessed by the Clinical Research Physician during medical review.

8.2.3 Statistical methods

8.2.3.1 Progression Free Survival

In the per protocol population:

PFS will be compared between trabectedin and control arm when 71 PFS events are observed. A Cox regression model including treatment and stratification factors at randomization (except institution) will be fit. If for a factor, Proportional Hazards assumptions (PH) are not respected (assessed by Schoenfeld residuals), the model will be stratified (i.e. not adjusted) by this factor. The superiority of trabectedin against the control arm will be tested at 10 % one-sided (20% two-sided) significance level. The treatment HR estimate will be presented with 90 % one-sided confidence interval (CI). 95% CI will also be presented. The PFS probability at 6 months (PFS-6) and the median PFS (mPFS) will be extracted from the Kaplan-Meyer PFS curve. 95% confidence intervals will be computed based on the Greenwood's formula. For the median the Reflected Method will provide 95% confidence intervals.

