- ◆ No known MRI or CT, including contrast media, contraindications
- ◆ Absence of any psychological, familial, sociological or geographical condition potentially hampering compliance with the study protocol and follow-up schedule; those conditions should be discussed with the patient before registration in the trial
- ◆ Before patient randomization, written informed consent must be given according to ICH/GCP, and national/local regulations.

Important note: All eligibility criteria must be adhered to, in case of deviation discussion with Headquarters and study coordinator is mandatory.

4 Trial Design

This is a randomized open label multicenter comparative phase II trial. The Korn design (Ref. 10) will be applied (for detailed statistical considerations see chapter 8).

[figure not shown]
Patients will be randomized at the EORTC headquarters after verification of the eligibility criteria (see chapter 3) to receive one of the following:

- ◆ Arm 1 (treatment): Trabectedin delivered as a 24-hour infusion every 3 weeks (day 1 of each 21-day cycle) at a starting dose of 1.5 mg/m² body surface area (BSA), until one of the treatment withdrawal criteria has been met.
- ◆ Arm 2 (control): Local standard of care.

For the trabectedin arm one cycle will be defined as 3 weeks.

For the control arm one cycle will be defined according to the treatment schedule of the chosen drug.

Disease will be assessed by the Macdonald response criteria (see chapter 7).

5 Therapeutic regimens, expected toxicity, dose modifications

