8.2.3.2 Radiological response

In the per protocol population:

The best overall response will be presented in contingency table with numbers and percentages. The objective response (CR/PR) and complete response rates will be reported with exact (binomial) 95% confidence interval. The medians of objective (PR/CR) and complete (CR) response duration will be extracted from their respective Kaplan-Meier curves. The Reflected Method will provide 95% confidence interval.

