8.2.3.3 Overall Survival

In the per protocol population:

OS will be compared between trabectedin and control arm. A Cox regression model including treatment and stratification factors at randomization (except institution) will be fit. If for a factor, Proportional Hazards assumptions (PH) are not respected (assessed by Schoenfeld residuals), the model will be stratified (i.e. not adjusted) by this factor. The superiority of trabectedin against the control arm will be tested at 5% two-sided significance level. The treatment HR estimate will be presented with 95% CI. The OS probability at 6 months (OS6), at 1 year (OS12) and the median OS (mOS) will be extracted from the Kaplan-Meyer OS curve. 95% confidence intervals will be computed based on the Greenwood's formula. For the median the Reflected Method will provide 95% confidence intervals.

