8.2.4 Pre-planned sensitivity or exploratory analyses

There is no pre-planned sensitivity analysis. Exploratory analyses may be performed on the basis of subgroup of patients (e.g. Ki67 expression, microvascular density, and density of tumor-associated macrophages), but results of these exploratory analyses may not serve as a basis for drawing conclusions concerning protocol treatment efficacy, and the reasons for excluding patients should be clearly reported.

Below a power table. It assumes worse prognosis in a high proliferation subgroup. Different rates of high proliferation and prognostic detrimental effect (HR>1) are computed.

Power to show the prognostic effect of a proliferation index in the whole population with 71 PFS events at 2.5% significance (one-sided).

	Hazard Ratio			
High proliferation rate	HR=1.95	HR=2	HR=2.5	HR=3.05
10%	<80%	41.5%	63.5%	80%
20%	<80%	64.5%	87%	>80%
30%	<80%	76%	94%	>80%
40%	<80%	81.5%	96.5%	>80%
50%	80%	83%	97%	>80%

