10.4.1 Missing data

Missing data is a potential major source of bias in HRQoL assessment.

In order to check the potential impact in the study, the compliance mechanism will be investigated prior to initiating the HRQoL analysis. Characteristics of patients with and without valid HRQoL data will be compared and trends over time per dropout pattern will be investigated. Model building will be used in order to investigate whether the compliance mechanism is linked to selected prognostic variables.

Once the main analysis is completed, sensitivity analyses will be undertaken to verify the robustness of the results vis-à-vis the missing data by imputation of plausible values. In case overall compliance is deemed too low (<50%), only an exploratory analysis will be performed in lieu of the main analysis.

11 Translational research

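### PFS, response and OS are analysed only per protocol; the ITT set is assigned to no analysis, so no planned efficacy result would show the effect of exclusions made after open-label allocation

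*Combined protocol and SAP*

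**What the plan says.** Section 8.2.2 defines three sets. The first is "Intention-to-treat population: all randomized patients will be analyzed in the arm they were allocated by randomization". The per-protocol set is narrower: eligible patients who received at least one dose of trabectedin or started local standard of care. Any deviation from the chapter 3 criteria makes a patient ineligible, and "Potential eligibility problems will be assessed by the Clinical Research Physician during medical review".

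The sets are then used as follows:

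- **PFS (8.2.3.1), response (8.2.3.2) and OS (8.2.3.3):** each section opens with "In the per protocol population". Under that heading come the PFS test, the response tables ("The best overall response will be presented in contingency table with numbers and percentages") and the OS test ("OS will be compared between trabectedin and control arm").
- **Safety (8.2.3.4):** the safety set, with laboratory and adverse events of never-starters reported separately.
- **Interim analysis (8.3) and the RANO/Macdonald comparison (11.2):** no set is named.
- **Sensitivity analyses:** 8.2.4 states "There is no pre-planned sensitivity analysis". The only ones in the document are in 10.4.1 ("Once the main analysis is completed, sensitivity analyses will be undertaken"), and they concern missing quality-of-life data.

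On design, section 4 states "This is a randomized open label multicenter comparative phase II trial". Chapter 6 accepts a delay of up to 21 days between randomization and treatment start.

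**The concern.** Starting treatment is a condition met, or not met, after randomization and with the arm known to patient and investigator. Eligibility is checked item by item before allocation (chapter 13), but the judgement that decides membership of the per-protocol set comes later, at medical review, and the plan does not say that it is blind to arm or outcome. Exclusions could therefore differ between arms and be related to prognosis. A comparison restricted in that way no longer rests on the randomization alone.

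Deaths before the first dose are a specific case. They are events for PFS (7.1.3) and OS (7.1.4), both counted from randomization, yet such patients drop out of both analyses.

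The result is meant to decide whether phase III or adjuvant development is justified (2.1). If the plan is followed as written, nothing in the efficacy output would separate harmless exclusions from ones that move the hazard ratio.

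**Working it through.** **1. The plan's own figure.** HR = ln(0.35)/ln(0.15) = 0.5534. Schoenfeld's formula at one-sided 10%, 85% power and 2:1 allocation:

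(1.2816 + 1.0364)² / [(2/3)(1/3) × (ln 0.5534)²] = 5.373 / (0.2222 × 0.3501) ≈ 69.1, so 70 events.

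Section 8.1.1 states 72, which is consistent. The 86 patients (57 + 29) are per-protocol patients. The number randomized is not given: with 5% or 10% excluded it would be 86/0.95 ≈ 91 or 86/0.90 ≈ 96.

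**2. Effect of selective exclusion when there is no treatment effect.** Exclusion rates and selection strength are assumptions.

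- Accrual as in 8.1.1; PFS-6 of 15% in both arms; progression detected on a 9-week grid; 10% of events taken as deaths at their exact time.
- Prognostic log-hazard SD 0.5-0.7, half of its variance carried by three binary factors standing for grade, age and performance status.
- Excluded patients drawn at random from the worse half (trabectedin) or the better half (controls).
- Cut at the 72nd per-protocol event; one-sided 10% Wald test from a Cox model; 5,000 trials per cell (Monte Carlo SE 0.4-0.7 points).

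| Exclusion | Unadjusted | Adjusted for the three factors |
|---|---|---|
| None | 10.1% | 9.9-11.3% (repeat runs of the same set-up) |
| Random, 10% of both arms | 10.1% | – |
| 5% of trabectedin | 10.9-11.8% | 10.9-11.6% |
| 10% of trabectedin | 12.6-13.4% | 11.3-12.0% |
| 10% of controls | 12.9-13.6% | 11.4-12.0% |
| 20% of controls | 15.5-19.3% | 12.5-15.0% |
| 10% of one arm, opposite direction | 7.1-7.9% | – |

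The adjusted column is the relevant one, because 8.2.3.1 specifies a Cox model with the stratification factors other than institution. An ITT analysis at the same cut-off, with everyone followed to progression, rejected in 9.0-10.9% in every scenario. Using 71 events (8.2.3.1) instead of 72 (8.1.1) made no difference beyond simulation error.

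**3. A different model.** Half the patients are slow and half fast progressors, with hazards differing 2- to 4-fold; log-rank test, 71 events, no adjustment. Exclusions are given as control / trabectedin.

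- Random exclusion: 9.5-9.9%.
- Slow progressors excluded: 11.1-12.8% (10% / 3%), 12.8-17.3% (15% / 3%), 14.6-20.4% (20% / 5%).
- Fast progressors excluded, 10-20% / 3-5%: 4.9-8.0%.
- Equal 5% selective exclusion in both arms: 9.2-10.4%.
- ITT: 9.1-9.6% throughout.

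**4. Deaths before the first dose.** With exponential survival at the 7- to 13-month medians quoted in 1.1, the proportion dying within 21 days is 1 − exp(−ln 2/median × 21/30.44): 3.6% at 13 months and 6.6% at 7 months, or about 3-6 of 91-96 patients. With a 7-day wait it is 1.2-2.3%, or 1-2 patients. The 9-week life-expectancy criterion in chapter 3 makes these upper figures.

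**5. How much ITT restores under the plan's censoring rule.** Section 7.1.3 censors PFS at the start of new anti-tumour therapy. With 20% of controls excluded, if 50% / 100% of never-starters are censored for that reason in weeks 3-12, unadjusted ITT rejection is 12.0-13.2% / 14.0-16.4%, against 15.5-19.3% per protocol. The correction is then only partial.

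**6. Cost in power.** If 5% / 10% of trabectedin patients never start and progress like controls, the ITT hazard ratio is 0.573 / 0.586 with 74.7 / 77.4 events, and ITT power is 84.3% / 82.9%. Per-protocol power in the same runs is 86.0-86.6%.

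**The case against.** The strongest reply is that the effect is small in the model the plan actually uses. The adjusted test already rejects in about 10-11% of null trials without exclusions, so selection of 5-10% in one arm adds only about 0-2.5 points. Adding the futility stop in 8.3 to the adjusted model gives 9.4-10.5% without exclusions, 10.7-11.8% with 5-10% excluded from one arm, and 13.3-13.5% with 20% of controls excluded. The harmful scenarios require exclusions that are unequal and in trabectedin's favour. Losing 20% of controls means about 7 patients (29/0.80 ≈ 36 randomized), although a control need only start a therapy of the investigator's choosing. Eligibility follows written criteria and is checked before allocation. Early deaths bias the hazard ratio only if waiting time or selection differs by arm.

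All of this stands as a limit on size. It does not answer the point. The plan states no exclusion rate and no planned efficacy analysis would reveal one scenario from another. An ITT analysis chosen after the data are seen carries less weight than one specified now. The separate listing of never-starters in 8.2.3.4 covers laboratory and adverse events, not their effect on the hazard ratio.

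It is also true that per protocol is a defensible primary set here, given the activity objective and the sample-size definition. Nothing below changes that. The unstated blinding of the eligibility review is missing detail, and the conclusion does not depend on it.

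**Conclusion.** The concern holds and should be fixed. Followed as written, the plan yields no efficacy result in the randomized population. This is a gap in the plan, not evidence that bias has occurred.

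Under the stated assumptions and the planned adjusted model, one-sided error would be about 11-12% for 5-10% selective exclusion in one arm, hardly above the adjusted baseline, and about 13-15% for 20% of controls. In a 10,000-trial repeat of that last scenario the rate was about 14.1% against 10.0-11.1% without exclusions, an increase of 3-4 points. Unadjusted figures are higher (about 11-14% and 16-19%). The error falls below 10% if selection runs the other way, and is unaffected by random exclusion. Direction and size depend on exclusion numbers that the documents do not give.

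**What to change.** 1. **8.2.3.1, 8.2.3.3, 8.2.4:** pre-specify an ITT analysis of PFS and OS (all randomized, as allocated, same Cox model and data cut-off), reported beside the per-protocol result as supportive, with a table of exclusions by arm, reason and timing.
2. **8.2.3.2:** also tabulate response in all randomized patients, using the categories that 7.1.5 already assigns to everyone.
3. **Follow-up and censoring:** reconcile the heading of 6.4.3, which ends assessment at progression or new therapy, with 6.3.1 and 7.1.2.1, which describe 9-weekly MRI regardless of delays and from randomization until progression, so that follow-up of never-starters is clear. Add an ITT PFS sensitivity analysis that does not censor at new therapy where later progression or death is recorded.
4. **8.2.2:** state that eligibility is judged blind to arm and outcome. This is a useful clarification, secondary to the items above.

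The cost is wording, a few model runs and follow-up of never-starters: about 5-10 patients if 5-10% of 91-96 never start. Scans and survival follow-up are already described. The primary test, its events and its power are unchanged. The price is a diluted ITT hazard ratio (about 0.57-0.59 instead of 0.55) with 83-84% power, which is why it should be read as supportive.

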8.3 Interim analyses

A futility interim analysis based on boundaries from Rho family ($\rho=1.625$) is planned when half of events (36) are observed. This should occur about 14.5 months after start of accrual when 61 patients are recruited. In absence of effect i.e. an observed PFS HR ≥ 1 , trial would be stopped for futility. With this boundary, there is 50% chance to stop the trial for lack of effect if the null hypothesis is true (H0). Safety will be reviewed by the EORTC DSMB every 6 months and by the EORTC IDMC at the time of futility analysis together with efficacy data.

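### The primary PFS analysis is triggered at 71 events, one fewer than the 72 that the sample-size section says are needed, and nothing explains the difference

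*Combined protocol and SAP*

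**What the plan says.** All references are to the combined protocol and SAP.

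**Places that give or imply 72**
- Section 8.1.1 (Sample size): "a power equal to 85%, 72 progressions or deaths are needed to assess the targeted effect".
- Protocol summary, patient-number row: the same requirement of 72 progression or death events.
- Section 8.3 (Interim analyses): the futility look is "planned when half of events (36) are observed", which is exactly half of 72.

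**Places that give 71**
- Section 8.2.3.1 (Progression Free Survival): the arms are compared "when 71 PFS events are observed".
- Protocol summary, statistical methods row: the same trigger.
- Section 8.2.4, heading of the prognostic power table: "with 71 PFS events at 2.5% significance (one-sided".

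The summary thus contains both figures. No section says that 72 is a planning target and 71 a deliberate operating value.

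**The concern.** In an event-driven trial the event count fixes the primary data cut. Here it also feeds section 8.4, which makes the end of study depend on the trial being mature for the primary analysis as the protocol defines it, and section 9, which withholds efficacy results until the data are mature. At 71 events the analysis follows 8.2.3.1 but falls short of the number that 8.1.1 says is needed. If the team waits for 72, it departs from 8.2.3.1. The trial is open label and progression is assessed at the treating site, so such a discrepancy is better closed before the data are seen.

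Each number recurs in running text in more than one section, so this is not a single misprint.

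**Working it through.** **Inputs (8.1.1, 8.3).** One-sided alpha 10%, power 85%, 2:1 allocation. On the rates, "PFS-6=15% was assumed in the control arm and 35% in the trabectedin arm", and "this corresponds to a treatment Hazard Ratio (HR) equal to 0.55". Under exponential PFS the unrounded value is ln(0.35)/ln(0.15) = 0.5534. The futility rule stops the trial if the observed HR is 1 or more at 36 events.

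**1. Reproducing the plan's figure.** Schoenfeld's formula with 2:1 allocation is

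d = (z₀.₉₀ + z₀.₈₅)² / [(2/3)(1/3)(ln HR)²], with (1.2816 + 1.0364)² = 5.373.

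- HR 0.5534: 5.373 / (0.2222 × 0.3501) = 69.06, so 70 events.
- HR 0.55: 5.373 / (0.2222 × 0.3574) = 67.65, so 68 events.

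The plan's 72 is within 2 of the first result. Adding a beta-spending futility look at half information (rho = 1.625) gives these event counts:

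| HR | Binding boundary | Non-binding boundary |
|---|---|---|
| 0.5534 | 71.3 | 73.2 |
| 0.55 | 69.8 | 71.7 |

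Both 71 and 72 lie within this range. That 72 comes from a futility-adjusted calculation is an inference from the numbers; 8.1.1 cites only the logrank test.

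**2. Power at each count.** Without the look, power = Φ(√(2d/9) × |ln HR| − 1.2816). For 71 events at HR 0.5534 this is Φ(2.3504 − 1.2816) = 85.7%. For 72 it is Φ(2.3669 − 1.2816) = 86.1%. With the look, power is P(Z₁ > 0 and Z₂ > 1.2816), where Z₁ and Z₂ are bivariate normal with correlation √(36/d).

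| HR | Futility look | 71 events | 72 events | Difference (points) |
|---|---|---|---|---|
| 0.5534 | no | 85.7% | 86.1% | 0.4 |
| 0.5534 | yes | 84.4% | 84.7% | 0.3 |
| 0.55 | no | 86.3% | 86.6% | 0.4 |
| 0.55 | yes | 84.9% | 85.2% | 0.3 |

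Differences are taken before rounding. The final test is at one-sided 10% for either count.

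**3. Interim fraction.** 36/72 = 50.0%; 36/71 = 50.7%.

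**4. Which count the 8.2.4 table used.** Power = Φ(√(d·p(1−p)) × ln HR − 1.960), where p is the high-proliferation share. At HR = 2:

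| p | Printed | 71 events | 72 events |
|---|---|---|---|
| 10% | 41.5% | 41.8% | 42.2% |
| 20% | 64.5% | 64.7% | 65.3% |
| 30% | 76% | 76.3% | 76.9% |
| 40% | 81.5% | 81.6% | 82.2% |
| 50% | 83% | 83.2% | 83.7% |

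The printed values fit 71 better, so 71 was apparently used in that calculation and not only in its heading.

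**5. Time between the two events.** The plan's accrual rates give 86 patients at about month 18.0. With exponential PFS at 15% and 35% at six months and no loss to follow-up, 36 events are expected at month 14.5, which agrees with 8.3. Event 71 is expected at about month 21.4 and event 72 at about month 21.7, roughly 10 days later.

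**The case against.** The strongest reply is that this is editorial. Both sentences that say when PFS will be compared agree on 71, and 72 appears only as the number needed, never as a trigger. Either count is compatible with the design calculation, and the two differ by a fraction of a percentage point and some 10 days. All of this stands, and it keeps the point minor.

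It also rules out three stronger readings that a reader might infer:

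- **That 71 events leave the trial short of its stated power while 72 would restore it.** On the logrank basis that 8.1.1 describes, both counts exceed 85%. With the futility look at HR 0.5534, both fall slightly below it. Only with the rounded HR of 0.55 and the look included does 85% lie between them (84.9% and 85.2%).
- **That the interim at 36 events excludes 71.** Half of 71 is 35.5, which rounds up to 36. The interim is exactly half of 72 but is also compatible with 71.
- **That the plan offers two data cuts to choose from.** It states one trigger, 71. The fault is that this trigger does not match the stated requirement.

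What the reply does not supply is a reason for the difference. The documents give none.

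**Conclusion.** The plan is wrong as written, as a minor internal inconsistency in the primary-analysis trigger: the comparison is set one event below the number the plan says is needed. The effect is about 0.3 to 0.4 percentage points of power, with the significance level unchanged. It is not evidence of an underpowered design or of a selectable cut-off.

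The power figures assume proportional hazards, the Schoenfeld approximation with information of 2/9 per event, and, where the look is included, a stop whenever the observed HR at 36 events is 1 or more. The plan does not say whether its 85% includes that look. This matters more than the choice of count: including the look lowers power by about 1.3 to 1.5 points.

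**What to change.** State one event count throughout, in one of two ways.

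- **Use 72.** Change the trigger in section 8.2.3.1 and in the summary's statistical methods row to 72. In section 8.2.4, either recalculate the table for 72 events (changes of about 0.6 points or less) or leave it explicitly labelled as computed for 71. Changing only its heading to 72 would mislabel values that fit 71. Section 8.3 needs no change.
- **Use 71.** Restate section 8.1.1 and the summary's patient-number row as 71 events, and describe the 36-event interim in section 8.3 as about 50.7% information. The 8.2.4 table stays as it is.

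In either case, add one sentence to 8.1.1 saying whether the 85% power includes the futility look.

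The cost is wording, a small table update if 72 is chosen and the table is recalculated, and at most one more event.
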